We will report descriptive results for all outcomes (i.e., means and proportions by group). In all models, the predictor will be a dummy variable indicating whether the participant was randomized to one of the three intervention nutrition claim conditions. For predictions with Likert-style outcomes, we will run linear regression models, one for each outcome. We will examine skewness of the residuals and run ordinal models in sensitivity analyses if residuals are skewed, retaining the linear models if the pattern of results does not change. For predictions with dichotomous outcomes, we will use the same approach except with logistic regression. We will use the margins command in Stata for significance testing of control vs. each claim separately, as well as each claim compared to the other claims.

We will also report results when controlling for any participant demographic characteristics (including random assignment to two experiments conducted after the primary outcome, but before measurement of some of the secondary outcomes) found to be unbalanced across treatment arms in balance tests, if these results differ substantively from unadjusted results (i.e., changes in statistical significance or direction of effect).

We will examine whether the following participant characteristics moderate the effect claims on the primary outcome:

- a) Age of child shopping for (in years);
- b) Gender of parent (man vs. woman);
- c) Gender of child (boy vs. girl);
- d) Race/ethnicity of parent (White non-Hispanic vs. Black non-Hispanic vs. Hispanic);
- e) Low educational attainment (dichotomized based on sample distribution);
- f) Household income (dichotomized based on sample distribution);
- g) Child's frequency of consuming fruit drinks (above vs. at or below the sample median);
- h) Time spent looking at Nutrition Facts Panel of the beverage;
- i) Seeking vitamin C since COVID-19 pandemic

To test whether these characteristics moderate the effect of claims on selection, we will fit a series of logistic regressions models (one for each potential moderator), with trial arm, the moderator, and their interaction as predictors. We will probe significant interactions by calculating the marginal effect of nutrition claims on the outcome at different levels of the moderating variable. We will use a critical alpha of 0.05 and statistical tests will be two-tailed. We will correct for multiple comparisons.

Task 2

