Using G.Power 3.1.9.4, researchers estimate that with a sample of approximately 2,170, alpha of 0.05, and 80% power, researchers could detect a small effect for the task 1 primary outcome ($f=0.06$), in line with a prior study of the impact of claims on intentions to purchase fruit drinks.³⁵

SAFETY MANAGEMENT

Provided that this study is conducted completely online, and participants do not have any interactions with study staff there is no anticipation of adverse events. However, the investigators have provided an email to contact as well as the IRB contact information, on the consent form should a participant be concerned about any aspects of the research study.

DATA COLLECTION AND MANAGEMENT

The research study will not collect any identifying information from participants, and Qualtrics will be programmed to not collect IP addresses. Researchers will store the study data on a remote terminal server, and only research investigators and staff will have access to the data.

RECRUITMENT STRATEGY

The study will recruit participants through panel companies (Kantar and CloudResearch). The panel companies will let panel members know about the study and interested panel members will complete a survey screener to find out if they are eligible.

CONSENT PROCESS

To provide consent, individuals will first complete a survey screener in Qualtrics. If they are eligible for the study, they will be redirected to the study consent form. If the participant agrees to the consent form, they are informed that by continuing to the study, they are consenting to participate. The

consent process is completed entirely online, and at no point in the study do participants interact with the study team.

PLANS FOR PUBLICATION

The investigators plan to publish task 1 and task 2 as separate peer-reviewed papers. They will target public health peer-reviewed journals for manuscript submission.

REFERENCES

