# **Studying the impact of product packaging in a virtual store environment**

## **Hypotheses and Analytic Plan**

**NCT #04381481**

**Version Date: 5/8/2020**

## **Sample size**

We will collect survey responses until ~2,175 adult (18 years and older) participants residing in the United States have completed the survey. Participants will be parents of children ages 1-5, whose child consumed at least one fruit drink in the past week. About one-third of the sample will be white, non-Hispanic; one-third of the sample will be black, non-Hispanic; and, one-third of the sample will be any race(s), Hispanic.

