## **Task 1**

### **Predictions**

The aim of Task 1 is to examine how nutrition claims on fruit drink packaging influence US parents' selections, perceptions, and reactions. We have the following predictions:

1. Parents who see a nutrition claim on a fruit drink will be more likely to select the fruit drink (versus 100% fruit juice) than those who do not see a nutrition claim (primary outcome)
2. Parents who see a nutrition claim on a fruit drink will be more likely to select the fruit drink (versus water) than those who do not see a nutrition claim
3. Nutrition claims will lead to greater perceived appeal of fruit drinks
4. Nutrition claims will lead to greater interest in giving fruit drinks to one's child
5. Nutrition claims will lead to greater interest in consuming fruit drinks
6. Parents who see a nutrition claim will be more likely to hold the misperception that the fruit drink is 100% fruit juice
7. Parents who see a nutrition claim will be more likely to hold the misperception that the fruit drink does not have added sugar
8. Nutrition claims will lead to lower estimates of the amount of added sugar people think the product contains
9. Nutrition claims will lead to higher estimates of the percentage of fruit juice people think the product contains
10. Nutrition claims will lead to lower perceived harm of fruit drinks compared to soda
11. Nutrition claims will lead to lower perceived harm of fruit drinks compared to 100% fruit juice
12. Nutrition claims will lead to greater misleadingness of the product packaging

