### **Analyses**

We will report descriptive results for all outcomes (i.e., means and proportions by group). In all models, the predictor will be a dummy variable indicating whether the participant was randomized to one of the three intervention nutrition claim conditions. For predictions with Likert-style outcomes, we will run linear regression models, one for each outcome. We will examine skewness of the residuals and run ordinal models in sensitivity analyses if residuals

are skewed, retaining the linear models if the pattern of results does not change. For predictions with dichotomous outcomes, we will use the same approach except with logistic regression. We will use the margins command in Stata for significance testing of control vs. each claim separately, as well as each claim compared to the other claims.

We will also report results when controlling for any participant demographic characteristics (including random assignment to two experiments conducted after the primary outcome, but before measurement of some of the secondary outcomes) found to be unbalanced across treatment arms in balance tests, if these results differ substantively from unadjusted results (i.e., changes in statistical significance or direction of effect).

We will examine whether the following participant characteristics moderate the effect claims on the primary outcome:

- a) Age of child shopping for (in years);
- b) Gender of parent (man vs. woman);
- c) Gender of child (boy vs. girl);
- d) Race/ethnicity of parent (White non-Hispanic vs. Black non-Hispanic vs. Hispanic);
- e) Low educational attainment (dichotomized based on sample distribution);
- f) Household income (dichotomized based on sample distribution);
- g) Child's frequency of consuming fruit drinks (above vs. at or below the sample median);
- h) Time spent looking at Nutrition Facts Panel of the beverage;
- i) Seeking vitamin C since COVID-19 pandemic

To test whether these characteristics moderate the effect of claims on selection, we will fit a series of logistic regressions models (one for each potential moderator), with trial arm, the moderator, and their interaction as predictors. We will probe significant interactions by calculating the marginal effect of nutrition claims on the outcome at different levels of the moderating variable.

We will use a critical alpha of 0.05 and statistical tests will be two-tailed. We will correct for multiple comparisons.

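### Does the promised correction for multiple comparisons undercut the 80% power of the Task 1 primary test?

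*Protocol*

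**What the plan says.** The protocol (Sample Size and Power) gives one power statement: "with a sample of approximately 2,170, alpha of 0.05, and 80% power, researchers could detect a small effect for the task 1 primary outcome", at f=0.06. The SAP (Sample size) sets the target in completers: "We will collect survey responses until ~2,175 adult (18 years and older) participants residing in the United States have completed the survey".

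The SAP (Task 1, Predictions) labels only prediction 1 as the primary outcome. It reads in part "Parents who see a nutrition claim on a fruit drink will be more likely to select the fruit drink (versus 100% fruit juice", and the comparison group is parents who see no claim.

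The analysis text for Task 1 is nearly word for word the same in both documents:

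- On the model: "In all models, the predictor will be a dummy variable", which indicates assignment to any of the three claim conditions.
- On follow-up: Stata margins for "significance testing of control vs. each claim separately, as well as each claim compared to the other claims".
- On error control: "We will use a critical alpha of 0.05 and statistical tests will be two-tailed. We will correct for multiple comparisons". In the SAP these two sentences form their own paragraph after all Task 1 analyses. In the protocol they close the paragraph on moderators.

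Neither document names a correction method, defines a family, or states whether the primary test lies inside or outside the correction.

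**The concern.** Power is computed at 0.05, yet the plan says without qualification "We will correct for multiple comparisons". On the primary outcome alone one can count seven tests: the pooled any-claim test, three claim-versus-control contrasts and three claim-versus-claim contrasts. If the pooled test shared alpha with three or six others, its Bonferroni threshold would be 0.0125 or 0.0071, and the stated 80% would not apply.

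The choice could also decide the result. If the true effect is the design effect, the primary p-value would often lie between the stricter threshold and 0.05, and a rule settled after the data are seen would then settle the verdict. The opposite choice has a cost as well. With the pooled test at 0.05 and the six contrasts corrected only among themselves, the chance of at least one false positive on this outcome exceeds 5%.

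Last, a two-level dummy cannot yield claim-specific contrasts. A second model is needed, and nothing says whether it shares alpha with the first.

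**Working it through.** **Inputs.** N=2,170, f=0.06, alpha 0.05 and power 80% come from the protocol (Sample Size and Power). Two-sided testing and the list of contrasts come from the Task 1 analysis text. Three assumptions are not in the documents: equal allocation to the four drink versions (2,170/4 = 542.5 each, 1,627.5 for the three claims together), f weighted for that 1:3 split, and each correction method tried.

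**1. Reproduce the stated power.** For a one-degree-of-freedom F test, the noncentrality is λ = N·f² = 2,170 × 0.0036 = 7.81. Power at two-sided 0.05 is 79.8% (79.9% at N=2,175). Normal check: √7.81 = 2.795, and Φ(2.795 − 1.960) = Φ(0.835) = 79.8%. A four-group test on three degrees of freedom would give 64.2%. The stated 80% therefore matches the pooled any-claim test at an unadjusted 0.05.

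**2. Put the pooled test inside a corrected family.** The calculation is the same with a smaller alpha. The Holm and Benjamini-Hochberg figures are simulated with every claim at d = 0.06/√(0.25 × 0.75) = 0.139.

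| Assumed family | Bonferroni alpha | Bonferroni power | Holm | Benjamini-Hochberg |
|---|---|---|---|---|
| Primary test alone | 0.05 | 79.8% | – | – |
| Pooled + 3 claim vs control | 0.0125 | 61.6% | 64% | 70% |
| Pooled + all 6 contrasts | 0.0071 | 54.1% | 55% | 62% |

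Under the same assumptions the primary p-value lies between 0.0125 and 0.05 in 18% of trials, and between 0.0071 and 0.05 in 26%.

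**3. Ask whether the documents put it there.**

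- Prediction 1 is the only Task 1 prediction marked primary.
- The only alpha stated for Task 1 is 0.05.
- The power statement names the Task 1 primary outcome and uses 0.05. As step 1 shows, it matches a single unadjusted test of that prediction.
- The work that is multiple by nature (six contrasts, eleven further predictions, nine moderators) stands in the same sections as the promise to correct.
- No passage groups the pooled test with the contrasts. The pooled effect is, with equal groups, the average of the three claim-versus-control effects, so counting it as one more Bonferroni member would be unusual.

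These statements agree with one another when the primary test is run at 0.05 and the correction applies to the rest.

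**4. Test the tighter rule.** One could interpret the contrasts only if the pooled test is significant. When no claim works, the chance of at least one false positive on the primary outcome is 7.5% with the pooled test at 0.05 and six Holm-corrected contrasts without a gate, and 5% with the gate. The gate's cost depends on how effects are spread (power for one effective claim against control, Holm over six):

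| True effects | No gate | Gate |
|---|---|---|
| All three claims d=0.139 | 38% | 38% |
| One claim d=0.212, two at zero | 83% | about 30% |
| One claim d=0.170, two at zero | 59% | 20% |

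The second row can be checked by hand. The pooled effect is 0.212/3 = 0.0707, and its standard error is √(1/542.5 + 1/1,627.5) = 0.0496. The ratio is 1.425, so the gate opens with probability Φ(1.425 − 1.960) = about 30%.

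**The case for a change.** The strongest case for a change is that the exemption of the primary test is nowhere written. The SAP's correction sentence follows all Task 1 analyses, so it cannot be confined to the moderators, and the seven tests are counted from the plan's own list. Naming the method and family would take a few sentences and no participants.

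Much of this stands. The correction is under-described, and a moderator-only reading does not fit the SAP's layout. A published sentence would remove any doubt about when the rule was chosen. But the argument shows missing detail, not a stated figure that is wrong or two statements that conflict. The 62% and 54% hold only if the primary test is placed in a family that the documents do not form, and they are the lowest figures among the three methods tried.

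The 7.5% is the joint chance over the primary test and the follow-up contrasts. The single primary claim keeps its 5%. Bringing the joint figure to 5% by a gate could hide a single effective claim, and the protocol's Background names the effects of specific claim types as a gap in the evidence.

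The dummy wording is shorthand. The margins contrasts the plan asks for need a four-level claim factor, and an analyst running them would fit one.

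**Conclusion.** The concern does not call for a change. Read as a whole, the plan tests one labelled Task 1 primary prediction at two-sided 0.05, and its 80% power reproduces at 79.8%. The unnamed method and family concern the further comparisons. That is a gap analysts fill with a standard procedure, and it does not alter the primary test or the sample size.

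This rests on two conditions. First, the primary test is outside the correction, which is the plain reading but is not stated in so many words. If it were inside, power would be about 62% to 70% in a family of four and 54% to 62% in a family of seven, from Bonferroni to Benjamini-Hochberg. Second, f=0.06 is weighted for a 1:3 split, so that d=0.139. If it meant d=0.12, power at that split would be 67.7% before any correction: 0.12/0.0496 = 2.42, and Φ(2.42 − 1.96) = 67.7%. The power statement does not give the test or groups entered, so the second condition is inferred from the match. It is separate from multiplicity.

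A gate on the contrasts is a trade-off: nearly free if all claims work equally, and costly (83% to about 30%) if only one does.

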# **Studying the impact of product packaging in a virtual store environment**

## **Hypotheses and Analytic Plan**

**NCT #04381481**

**Version Date: 5/8/2020**

## **Sample size**

We will collect survey responses until ~2,175 adult (18 years and older) participants residing in the United States have completed the survey. Participants will be parents of children ages 1-5, whose child consumed at least one fruit drink in the past week. About one-third of the sample will be white, non-Hispanic; one-third of the sample will be black, non-Hispanic; and, one-third of the sample will be any race(s), Hispanic.

## **Interim analysis**

No interim analyses are planned.

## **Task 1**

### **Predictions**

The aim of Task 1 is to examine how nutrition claims on fruit drink packaging influence US parents' selections, perceptions, and reactions. We have the following predictions:

1. Parents who see a nutrition claim on a fruit drink will be more likely to select the fruit drink (versus 100% fruit juice) than those who do not see a nutrition claim (primary outcome)
2. Parents who see a nutrition claim on a fruit drink will be more likely to select the fruit drink (versus water) than those who do not see a nutrition claim
3. Nutrition claims will lead to greater perceived appeal of fruit drinks
4. Nutrition claims will lead to greater interest in giving fruit drinks to one's child
5. Nutrition claims will lead to greater interest in consuming fruit drinks
6. Parents who see a nutrition claim will be more likely to hold the misperception that the fruit drink is 100% fruit juice
7. Parents who see a nutrition claim will be more likely to hold the misperception that the fruit drink does not have added sugar
8. Nutrition claims will lead to lower estimates of the amount of added sugar people think the product contains
9. Nutrition claims will lead to higher estimates of the percentage of fruit juice people think the product contains
10. Nutrition claims will lead to lower perceived harm of fruit drinks compared to soda
11. Nutrition claims will lead to lower perceived harm of fruit drinks compared to 100% fruit juice
12. Nutrition claims will lead to greater misleadingness of the product packaging

### **Analyses**

We will report descriptive results for all outcomes (i.e., means and proportions by group). In all models, the predictor will be a dummy variable indicating whether the participant was randomized to one of the three intervention nutrition claim conditions. For predictions with Likert-style outcomes, we will run linear regression models, one for each outcome. We will examine skewness of the residuals and run ordinal models in sensitivity analyses if residuals

are skewed, retaining the linear models if the pattern of results does not change. For predictions with dichotomous outcomes, we will use the same approach except with logistic regression. We will use the margins command in Stata for significance testing of control vs. each claim separately, as well as each claim compared to the other claims.

We will also report results when controlling for any participant demographic characteristics (including random assignment to two experiments conducted after the primary outcome, but before measurement of some of the secondary outcomes) found to be unbalanced across treatment arms in balance tests, if these results differ substantively from unadjusted results (i.e., changes in statistical significance or direction of effect).

We will examine whether the following participant characteristics moderate the effect claims on the primary outcome:

- a) Age of child shopping for (in years);
- b) Gender of parent (man vs. woman);
- c) Gender of child (boy vs. girl);
- d) Race/ethnicity of parent (White non-Hispanic vs. Black non-Hispanic vs. Hispanic);
- e) Low educational attainment (dichotomized based on sample distribution);
- f) Household income (dichotomized based on sample distribution);
- g) Child's frequency of consuming fruit drinks (above vs. at or below the sample median);
- h) Time spent looking at Nutrition Facts Panel of the beverage;
- i) Seeking vitamin C since COVID-19 pandemic

To test whether these characteristics moderate the effect of claims on selection, we will fit a series of logistic regressions models (one for each potential moderator), with trial arm, the moderator, and their interaction as predictors. We will probe significant interactions by calculating the marginal effect of nutrition claims on the outcome at different levels of the moderating variable.

We will use a critical alpha of 0.05 and statistical tests will be two-tailed. We will correct for multiple comparisons.

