[show just the label] How much does this label make you concerned about the health effects of consuming this product?	1=Not at all 2=Very little 3=Slightly 4=Quite a bit 5=A great deal

How much does this label make consuming this product seem unpleasant to you?	1=Not at all 2=Very little 3=Somewhat 4=Quite a bit 5=A great deal
How much does this label discourage you from wanting to consume this product?	1=Not at all 2=Very little 3=Somewhat 4=Quite a bit 5=A great deal
How likely are you to talk about this label with others in the next week?	1 = Not at all likely 2 = A little likely 3 = Somewhat likely 4 = Very likely 5 = Extremely likely
Did you learn something new from this label?	1 = Yes 0 = No
How much does this label grab your attention?	1=Not at all 2=Very little 3=Somewhat 4=Quite a bit 5=A great deal
How much does this label make you feel scared?	1=Not at all 2=Very little 3=Somewhat 4=Quite a bit 5=A great deal
How much does this label make you think about the health problems caused by eating this snack?	1=Not at all 2=Very little 3=Somewhat 4=Quite a bit 5=A great deal
Other Outcomes: Process Measures	
I was able to imagine doing my real-life convenience store shopping in the online store.	1 = Strongly disagree 2 = Somewhat disagree 3 = Neither agree nor disagree 4 = Somewhat agree 5 = Strongly agree
The beverages I selected in the online store were similar to beverage purchases I would make for my [age] year old child in real life.	1 = Strongly disagree 2 = Somewhat disagree 3 = Neither agree nor disagree 4 = Somewhat agree 5 = Strongly agree
The online store reminded me of convenience stores that I've been to.	1 = Strongly disagree 2 = Somewhat disagree 3 = Neither agree nor disagree 4 = Somewhat agree 5 = Strongly agree

STATISTICAL CONSIDERATION

Statistical Methods

Task 1

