### Analyses

We will report descriptive results for all outcomes (i.e., means and proportions by group). In all models, the predictor will be a dummy variable indicating whether the participant was randomized to one of the two warning message conditions. For predictions with Likert-style outcomes, we will run linear regression models, one for each outcome. We will examine skewness of the residuals and run ordinal models in sensitivity analyses if residuals are skewed, retaining the linear models if the pattern of results does not change. For predictions with dichotomous outcomes, we will use the same approach except with logistic regression. We will use the margins command in Stata for significance testing of control vs. each warning message separately, as well as each warning message compared to each other. We will also report results when controlling for any participant demographic characteristics (including random assignment to experiments conducted before the primary outcomes) found to be unbalanced across treatment arms in balance tests, if these results differ substantively from unadjusted results (i.e., changes in statistical significance or direction of effect).

We will examine whether the following participant characteristics moderate the effect claims on the primary outcome:

- a) Age of child shopping for (in years);
- b) Gender of parent (man vs. woman);
- c) Gender of child (boy vs. girl);
- d) Race/ethnicity of parent (White non-Hispanic vs. Black non-Hispanic vs. Hispanic);
- e) Low educational attainment (dichotomized based on sample distribution);
- f) Household income (dichotomized based on sample distribution);
- g) Time spent looking at Nutrition Facts Panel of the snack;

To test whether these characteristics moderate the effect of warning messages on selection, we will fit a series of logistic regressions models (one for each potential moderator), with trial arm, the moderator, and their interaction as predictors. We will probe significant interactions by calculating the marginal effect of sugar warnings on the outcome at different levels of the moderating variable.

We will use a critical alpha of 0.05 and statistical tests will be two-tailed. We will correct for multiple comparisons.

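### The linear models for Likert outcomes name no protection against unequal variances across arms, so some pairwise tests are miscalibrated if arm SDs differ; for text versus graphic warnings the intervals are too narrow if the barcode arm varies less.

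*SAP*

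**What the plan says.** The model text is the same in both tasks (SAP, Task 1 and Task 2, Analyses; repeated in the protocol's Statistical Methods): "For predictions with Likert-style outcomes, we will run linear regression models, one for each outcome". Stata's margins command then supplies the pairwise tests. For Task 2 these are "significance testing of control vs. each warning message separately, as well as each warning message compared to each other"; for Task 1 they are "significance testing of control vs. each claim separately, as well as each claim compared to the other claims". The one planned model check is this: "We will examine skewness of the residuals and run ordinal models in sensitivity analyses if residuals are skewed". On error rates the SAP says "We will use a critical alpha of 0.05 and statistical tests will be two-tailed" and promises a multiplicity correction without naming a method.

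Neither document mentions robust standard errors, arm-specific variances or a check for unequal variance. Neither says in words that one variance will be shared; that is the default of a linear regression with no further specification.

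The Task 2 control is a neutral barcode label (protocol, Study Design). The label-reaction items, for example "How much does this label make you feel scared", are asked about that barcode as well as the two warnings, on a 5-point scale whose lowest category is Not at all (protocol, measurements section, Secondary measures: Task 2).

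**The concern.** A default linear model estimates one residual variance from all arms and uses it for every contrast. In a two-arm comparison with equal arms, unequal variances do little harm. Text versus graphic is different: it compares two arms out of three, and the barcode arm helps set the standard error although it is not being compared. Equal arm sizes do not remove that, and neither does a large sample.

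Unequal variances are plausible for some Task 2 items. The SAP predicts that warnings will score above the barcode on message effectiveness, attention, fear and thoughts of health problems. On a bounded scale, a control mean close to the lowest category implies a small control variance. The barcode arm would then pull the pooled variance below that of the warning arms, and differences between the two warnings would be declared significant too often. The skewness check is not aimed at this.

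At stake is the calibration of pairwise tests on the Likert secondary outcomes. The same applies to estimated teaspoons of sugar and percent juice if these are analysed linearly; the plan names no model for them.

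**Working it through.** **The plan's own figure.** The only numerical power statement (protocol, Sample Size and Power) is f = 0.06 at N of about 2,170, alpha 0.05 and 80% power. It reproduces as a contrast with one numerator degree of freedom (power 79.8%). It concerns the dichotomous Task 1 primary outcome and does not bear on this point. The documents give no SD or response distribution for any Likert item, so there is no plan figure to reproduce here.

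**Inputs.** From the SAP: N of about 2,175 and two-sided alpha 0.05. From the protocol: three snack versions and four drink versions. Assumed: equal allocation, giving 2,175/3 = 725 per snack arm and 2,175/4 = about 544 per drink arm; equal SDs in the two warning arms; and r = SD(barcode)/SD(warning), taken over a range.

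**Formulas, equal arm sizes.** In units of the warning variance, the pooled variance is (r² + 2)/3.
- Text versus graphic: model SE / true SE = sqrt((r² + 2)/3).
- Control versus one warning: model SE / true SE = sqrt(2(r² + 2)/(3(1 + r²))).
- Type I error = 2 × P(Z > 1.96 × ratio).

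| r | Text v graphic: SE ratio | Type I | Control v warning: SE ratio | Type I |
|---|---|---|---|---|
| 0.5 | 0.866 | 9.0% | 1.095 | 3.2% |
| 0.7 | 0.911 | 7.4% | 1.056 | 3.9% |
| 0.9 | 0.968 | 5.8% | 1.017 | 4.6% |
| 1.0 | 1.000 | 5.0% | 1.000 | 5.0% |
| 1.1 | 1.034 | 4.3% | 0.984 | 5.4% |
| 1.2 | 1.071 | 3.6% | 0.969 | 5.7% |

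The limit for text versus graphic as r goes to 0 is a ratio of 0.816 and a type I error of 11.0%.

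**Simulation check.** 5-point data under assumed distributions, 725 per arm, 40,000 runs, pooled-variance test of text versus graphic:
- control at the floor on a fear-type item (SD 0.72 against 1.36): 8.8%
- milder floor (1.12 against 1.34): 6.4%
- near-equal SDs (1.31 against 1.34; 1.22 against 1.21): 5.1% and 4.9%
- warnings at the floor on an intention item (1.32 against 1.19): 4.2%
- warnings near the ceiling on attention (1.37 against 1.14): 3.5%

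With arm-specific variances the rate is 4.9% to 5.1% in every scenario.

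**Single any-intervention dummy.** The SAP also describes one dummy for any warning or any claim, so the split is 1:k with k = 2 or 3. With s0 and s1 the control and intervention SDs, and sp² = (s0² + k·s1²)/(1 + k), true SE / model SE = sqrt((s0² + s1²/k) / (sp²(1 + 1/k))).
- Task 2, s0 = 1.00, s1 = 1.36: ratio 0.905, type I error 3.0%.
- Task 2, s0/s1 = 1.2: ratio 1.062, type I error 6.5%.
- Task 1, s0 = 1.2, s1 = 1.0: sp² = (1.44 + 3)/4 = 1.11; ratio = sqrt(1.7733/1.48) = 1.095; type I error 7.3%.
- Task 1 with the SDs swapped: ratio 0.914, type I error 3.2%.

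**Does the skewness check catch it?** Assume barcode responses of 70/15/8/4/3% (SD 1.00) and warning responses of 20/18/25/20/17% (SD 1.36). The text-versus-graphic type I error is 7.1%, yet residual skewness over all arms is only about 0.33, although it is 1.9 within the barcode arm.

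**Does a multiplicity correction remove it?** Taking Bonferroni over three pairwise tests as an illustration, a nominal 1.67% becomes 2.75% under the same distributions.

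**The case against.** The strongest objection is that direction and size rest on SDs the documents do not give. A reader might infer that the text-versus-graphic intervals are simply too narrow. The documents do not support that: with equal SDs nothing is wrong, and if warnings compress responses the intervals are too wide. The floor argument fits items about the label itself. It does not carry over to the items that show the snack (healthy, appealing, give, buy, eat), and even attention could go the other way. This objection stands, and the point is conditional for that reason.

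A reader might also infer that the trial's central pictorial-versus-text question is compromised. The protocol's Background (Task 2) calls that comparison unknown for purchasing behaviour. The in-trial measure of purchasing is the snack selection, which is dichotomous and analysed by logistic regression. None of the 15 Task 2 predictions in the SAP compares text with graphic. They set warnings against control, and those tests are conservative when the barcode arm varies less.

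Nor can a general inflation of error be claimed for Task 1. Every arm sees an ordinary drink package, so there is no floor mechanism, and swapping the assumed SDs takes 7.3% to 3.2%.

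The ordinal sensitivity model is a partial safeguard. Under the 70/15/8/4/3% and 20/18/25/20/17% distributions, the large-sample type I error of a proportional-odds text-versus-graphic test is 4.8%. But it is run only if residuals look skewed, the plan sets no threshold, and pooled skewness there is modest.

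Finally, the shared variance is inferred from the software default, not from a statement. That is fair, and it is a reason to state the variance estimator.

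**Conclusion.** The point holds in conditional form. The plan specifies linear regression without a variance estimator and draws contrasts over all arms from it; near-equal arms do not protect a contrast between two of them when the variance is pooled over all. If the barcode arm varies less than the warning arms, the text-versus-graphic type I error is about 5.8% to 9.0% for SD ratios of 0.9 to 0.5, and control-versus-warning tests fall to 4.6% to 3.2%. Above a ratio of 1 the directions reverse. So whenever the control SD differs from the warning SD, one kind of test rejects too often and the other too seldom. In Task 1 the direction cannot be stated.

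These figures assume equal allocation, equal SDs in the two warning arms and the software's default variance. Only non-dichotomous secondary outcomes are affected. This is a low-cost improvement to secondary analyses, not a threat to the primary results.

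**What to change.** Add one sentence to the Analyses section of each task in the SAP, and to the matching protocol text: every linear model for a Likert outcome uses heteroscedasticity-robust standard errors (for example Stata vce(robust)), and the margins contrasts are computed from that fit. Apply the same to teaspoons of added sugar and percent juice if they are analysed linearly. Keep the ordinal models as sensitivity analyses.

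The cost is one option in the code. With about 540 to 725 per arm, assuming equal allocation, the loss when variances are in fact equal is negligible.
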